9.7.2. Analysis of safety endpoints of interest

For the safety endpoints of interest, descriptive statistics, counts and proportions, cumulative incidence proportions, and crude incidence rates (i.e., number of events per person-years) and associated two-sided 95% confidence intervals will be calculated as appropriate. UC patients with a baseline history of an outcome of interest will be excluded from the calculation of the incidence rate for that particular outcome of interest (e.g. patients with a baseline history of malignancy will be excluded from the calculation of the incidence rate for malignancy).

Several subgroup analyses will be performed. These include (but are not limited to) stratification by:

- Tofacitinib dose (5 mg twice daily vs. 11 mg once daily vs. 10 mg twice daily vs. 22 mg once daily)
- Patient characteristics such as age at index date, including a subgroup analysis of patients <50 years vs. ≥50 years, and patients <65 years vs. ≥65 years
- For the outcomes of VTE and MACE, subgroup analysis of patients with ≥1 thrombosis risk factors (as defined in Section 9.3.1.1) vs. no thrombosis risk factors, and
- Key indicators of disease severity such as number of previous biologic treatments (i.e. prior biologic use vs. none; among those with prior biologic use, 1st biologic vs. 2nd biologic vs. ≥3 biologics)

This will be a time to first event analysis based on an index date defined for each cohort with appropriate censoring rules applied (based on therapy switches, end of study, etc.) for those

who do not experience an event by end of follow-up period. Rates will be expressed as the number of events/100 person-years of follow-up.

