9.7.4. Final Study Report

In the final study report, data on the utilization patterns of tofacitinib will be provided as described in Section 9.7.1. For the analysis of safety events of interest, there will be some but limited flexibility to add additional safety endpoints and stratification, and it will contain populated tables in line with shells to be provided in the SAP.

In the final report, for the active surveillance portion of the study, the tofacitinib cohort will be analyzed overall and stratified by patient age, dose (5 mg twice daily vs. 11 mg once daily vs. 10 mg twice daily vs. 22 mg once daily), previous biologics use, VTE risk factors such as history of hypertension, and potentially other agreed upon strata determined prior to analysis and included in SAP filed with Sponsor. The general analytic approach will be descriptive and include incidence rates of safety events of interest within the tofacitinib cohort and within the contextualization cohort of those initiating treatment with a biologic, stratified by class of biologic (TNFi vs. non-TNFi), number of previous biologic treatments, monotherapy and combination therapy. For additional contextualization purposes, incidence rates will also be estimated for the other treatment cohorts.

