In addition, due to limitations related to the database, all-cause mortality cannot be assessed since only in-hospital deaths are captured. This may result in an underestimation of the outcome as deaths occurring in other environments (e.g. home, institutions, etc.,) cannot be captured. Additionally, due to privacy concerns, in-hospital deaths cannot be directly captured in the database, and must be estimated via use of an algorithm which will developed as part of this study and will not be able to be validated for use in claims databases. As such, in-hospital deaths may not be accurately captured in this study. For acute events, a 90 day extension period is implemented in part to accommodate ongoing exposure to treatments with longer half lives, and in part to ensure that any subclinical or undiagnosed illness at time of end of treatment is captured. However, there is the possibility of potential misclassification of the exposure window for any treatments for which the half-life is shorter, leading to a potential underestimation of incidence rates for some outcomes.

As tofacitinib is a new UC medication, it is possible that patients treated with it will represent those with the most severe cases of disease, longer disease duration, history of multiple failed

UC therapies and physical comorbidities that place patients at risk for events. Channeling may present as increased rates of safety events of interest in the early phases of the study. Incidence rates from the contexualization cohorts may illuminate such channeling via stratification on key indicators of disease severity such as number of previous biologic treatments, patient characteristics and past therapies. However, certain patient characteristics which may influence VTE risk (e.g. obesity and immobilization), cannot be reliably captured, and thus may limit data interpretation. Trend analyses may be conducted to evaluate rates in tofacitinib patients over time. Analysis may be unable to identify or control for any changes in rates due to changes in the treatment landscape.

Conclusions from this study may be limited to the duration of treatment captured. Finally, while these data may be generalizable to the commercially insured population and patients on Medicare, they may not be representative of those whose primary insurance is through Medicaid.

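### The final-report section names age strata for the tofacitinib cohort only, although the analysis and limitations sections point to wider use, and no age-standardised rate is planned for reading the four cohorts together

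*Protocol*

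**What the plan says.** Section 8 sets up Cohorts 2 to 4 (biologics, immunomodulators/immunosuppressants, naïve) to put the tofacitinib rates in context and to characterise risk. It expects the naïve cohort to have milder disease than the other three.

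Four sections bear on how the rates are to be read together:

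- **9.7.2 (analysis).** The measure is "crude incidence rates (i.e., number of events per person-years"), and "associated two-sided 95% confidence intervals will be calculated as appropriate". The unit is fixed: "Rates will be expressed as the number of events/100 person-years of follow-up". The subgroup list includes "Patient characteristics such as age at index date, including a subgroup analysis of patients <50 years vs. ≥50 years", then a second split at 65. Neither split is limited to a cohort.
- **9.7.3 (interim reports).** Overall crude rates, with no strata.
- **9.7.4 (final report).** Strata are given cohort by cohort. For Cohort 1, "the tofacitinib cohort will be analyzed overall and stratified by patient age, dose", previous biologic use and VTE risk factors. For Cohort 2, rates are given "within the contextualization cohort of those initiating treatment with a biologic, stratified by class of biologic (TNFi vs. non-TNFi), number of previous biologic treatments", and by monotherapy or combination therapy. For the remaining cohorts, rates are to be estimated and no stratum is named.
- **9.9 (limitations).** "Incidence rates from the contexualization cohorts may illuminate such channeling via stratification on key indicators of disease severity"; the sentence goes on to name patient characteristics and past therapies as well.

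Age and sex are baseline variables for everyone (9.3.1). Sex is not named as a stratum for the rates, and the protocol names no standardised or adjusted rate.

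**The concern.** The contextualisation cohorts are useful only if their rates can be set beside the tofacitinib rate. Malignancy, the primary outcome, normally rises with age, as do MACE and VTE. The cohorts are also built differently. Cohort 4 is indexed at UC diagnosis (9.3.4.2), whereas most tofacitinib users are expected to have had earlier UC therapy (9.2.1.2.1). There is no reason to expect the same age mix in each.

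An age-specific tofacitinib rate has nothing to be read against if the other cohorts have no matching rate. The two overall crude rates then remain, and their difference mixes any drug-related difference with age composition. A real excess could be hidden, or a false one shown. Section 12 foresees the results going to regulators, so readers will make this comparison whether or not the protocol defines a formal contrast.

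Both interim milestones in section 6 (June 2022 and June 2024) fall before the date of version 3.0 (30 September 2024). In practice the point bears on the final report.

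**Working it through.** **Step 1: set the sections side by side.**

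| Cohort | Age strata under 9.7.2 | Age strata named in 9.7.4 | Other strata named in 9.7.4 |
|---|---|---|---|
| 1 Tofacitinib | <50/≥50, <65/≥65 | Yes | Dose, previous biologics, VTE risk factors |
| 2 Biologics | Same list, not excluded | No | Class, number of previous biologics, mono/combination |
| 3 Immunomodulators/immunosuppressants | Same list, not excluded | No | None |
| 4 Naïve | Same list, not excluded | No | None |

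Sections 9.7.2 and 9.9 point one way and 9.7.4 the other. A programmer building tables from 9.7.4 would produce age strata for Cohort 1 only.

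**Step 2: how far can age mix alone move a crude rate?** The protocol states no age mix and no expected rate, so there is no figure of its own to reproduce. All inputs here are assumptions: 0.3 events per 100 person-years under 50 and 1.2 at 50 and over, identical in both cohorts, so there is no drug effect.

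Crude rate = (1 − p) × 0.3 + p × 1.2, where p is the share of person-time at 50 and over.

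| p, younger cohort | p, older cohort | Crude rates per 100 person-years | Ratio |
|---|---|---|---|
| 35% | 45% | 0.195 + 0.420 = 0.615; 0.165 + 0.540 = 0.705 | 0.87 |
| 30% | 50% | 0.210 + 0.360 = 0.570; 0.150 + 0.600 = 0.750 | 0.76 |
| 25% | 55% | 0.225 + 0.300 = 0.525; 0.135 + 0.660 = 0.795 | 0.66 |

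With equal shares (35% in both) the ratio is 1.00.

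**Step 3: vary the age gradient.** Keep 0.3 under 50 and let the rate at 50 and over be 2 to 8 times that. The mildest case (gradient 2, 35% against 45%) gives 0.405/0.435 = 0.93. The most extreme case tried (gradient 8, 25% against 60%) gives 0.825/1.560 = 0.53.

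**Step 4: what standardisation does.** The standardised rate is the sum over age bands of w × (band rate), with the same weights w for both cohorts. When the band rates are identical, the standardised rates are identical and the ratio is 1.00 in every scenario above.

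**Step 5: is one cut at 50 enough?** Suppose that, within the 50-and-over band, the rate at 65 and over is 2 to 3 times that at 50 to 64.

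- Ratio 2, share aged 65 and over 15% against 25%: (0.75 + 2 × 0.25)/(0.85 + 2 × 0.15) = 1.25/1.15 = 1.09.
- Ratio 3, share 15% against 40%: (0.60 + 3 × 0.40)/(0.85 + 3 × 0.15) = 1.80/1.30 = 1.39.

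A single split therefore leaves some age effect inside the upper band. Section 9.7.2 lists the two cuts as separate two-level splits.

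**Step 6: sex.** With a rate ratio between the sexes of 1.1 and shares of 45% against 55%, the crude ratio is 1.055/1.045 = 1.01. With 1.5 and 40% against 60% it is 1.30/1.20 = 1.08. Sex mix adds little compared with age.

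**The case against.** The strongest reply is that 9.7.2 already plans the age strata. It covers the safety endpoints with an index date for each cohort, and of its subgroup bullets only the dose one is specific to tofacitinib. A reader might infer from 9.7.4 that Cohorts 2 to 4 will be shown on crude overall rates with no age breakdown. The document does not support that reading: 9.7.4 does not exclude age strata elsewhere, it allows limited additions to the stratification, and it refers to table shells in the SAP. This part of the objection stands. The defect is an inconsistency between 9.7.2 and 9.9 on one side and 9.7.4 on the other, not a decision to forgo age strata.

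Second, the study is descriptive, tests no hypothesis and defines no contrast between cohorts. The primary objective is a rate in tofacitinib initiators, for which a crude rate is valid. That also stands, and nothing here questions the primary estimate. It does not settle how the contextual rates are read, because a standardised rate is just as descriptive and needs no test.

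Third, standardisation may be left to the SAP, which is not at hand and may provide it. Its absence from the protocol is therefore not an error in itself. But 9.7.4 allocates strata to cohorts, and that text needs reconciling with 9.7.2 and 9.9 whatever the SAP says.

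Finally, the age shares and rates in the illustration are assumed. That is correct, and neither the direction nor the size of any distortion can be derived from the protocol.

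**Conclusion.** The point holds as an internal inconsistency together with a worthwhile improvement. Section 9.7.4 does not schedule, for Cohorts 2 to 4, the age strata that 9.7.2 lists generally. It also does not schedule all the stratification that 9.9 relies on to reveal channelling. All named rates are crude.

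Under the main assumed rates, with no drug effect, age mix alone gives ratios of 0.87 to 0.66. Across the wider range of gradients and mixes tried, it gives 0.93 to 0.53. These figures rest wholly on assumed rates and age shares. If the cohorts turn out to have the same age mix, the distortion vanishes.

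Two stronger readings should be resisted. Sex mix is not a material driver on its own (1.01 to 1.08 under assumed inputs). Nor would age standardisation make the cohorts comparable in general: channelling by severity or prior therapy would remain, as 9.9 acknowledges it may.

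**What to change.** 1. In 9.7.4, state that the age strata of 9.7.2 (<50/≥50 and <65/≥65) apply to all four cohorts.
2. In 9.7.2 and 9.7.4, add a directly standardised rate with a 95% confidence interval beside each crude rate for malignancy excluding NMSC, MACE, VTE and serious infection. Take the weights from Cohort 1's person-time by age, and by sex since it is already collected. Combining the two existing cuts into three bands (<50, 50–64, ≥65) deals with the residual effect in step 5. With these weights Cohort 1's standardised rate equals its crude rate, so the primary estimate does not change.
3. State an event count below which the standardised rate is suppressed.
4. Keep channelling by severity and prior therapy as a stated limitation in 9.9, and say that standardisation does not remove it.

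The cost is a little programming and one extra column per table. No new data are needed. The drawback is that standardised rates are unstable for rare events and thin age-by-sex cells, which the suppression rule is meant to contain.

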9.7.3. Interim Reports

Interim reports assessing tofacitinib utilizations patterns to-date and summarizing the crude incidence rates (with corresponding 95% confidence intervals) of safety events of interest will be provided as per the timeline in Section 6 (Milestones). These will include data on UC patients treated with tofacitinib and other approved systemic medications, and rates "on drug" and "ever since treatment start" accumulated in Marketscan to date. Only overall (non-stratified) results will be provided.

9.7.4. Final Study Report

In the final study report, data on the utilization patterns of tofacitinib will be provided as described in Section 9.7.1. For the analysis of safety events of interest, there will be some but limited flexibility to add additional safety endpoints and stratification, and it will contain populated tables in line with shells to be provided in the SAP.

In the final report, for the active surveillance portion of the study, the tofacitinib cohort will be analyzed overall and stratified by patient age, dose (5 mg twice daily vs. 11 mg once daily vs. 10 mg twice daily vs. 22 mg once daily), previous biologics use, VTE risk factors such as history of hypertension, and potentially other agreed upon strata determined prior to analysis and included in SAP filed with Sponsor. The general analytic approach will be descriptive and include incidence rates of safety events of interest within the tofacitinib cohort and within the contextualization cohort of those initiating treatment with a biologic, stratified by class of biologic (TNFi vs. non-TNFi), number of previous biologic treatments, monotherapy and combination therapy. For additional contextualization purposes, incidence rates will also be estimated for the other treatment cohorts.

9.8. Quality Control

A series of automated and semi-automated procedures will be used to assess the validity and consistency of the study dataset.

For raw data, the number of unique patients and unique records for each year will be evaluated. The number of unique patients, and unique records, will be compared year-by-year and file-by-file, to ensure relative stability of counts over time. Each variable in the dataset will be examined for completeness vs. missingness, allowable values (verified against the data dictionary, as appropriate), and range checks. These checks will enable identification of both *errors* (systematic transformation issues) and *anomalies* (unexpected data behavior).

Following analyses, all output will be verified against source document(s). Source data may be in final (or draft) production reports generated by analytic procedures (e.g. SAS).

9.8.1. Methods to correct inconsistencies or errors

Summary statistics will be tabulated for all variables and outliers identified. Outliers will be reconciled with additional electronic data sources, when available.

9.8.2. Methods to address missing data

Imputation for missing data points will not be performed in this descriptive study.

9.9. Limitations of the research methods

This study is designed to assess to facitinib utilization patterns, as well as monitor its safety among US adult UC patients within the clinical practice setting using an administrative healthcare claims database. Strengths of the study include a large, demographically diverse cohort of UC patients allowing for the generation of robust incidence estimates for the various outcomes of interest.

Misclassification of exposure and endpoints and inability to obtain detailed clinical information are possible limitations due to the nature of claims databases. In addition, because the claims are collected for the purpose of payment and not research, in the case of drug administrations identified in the pharmacy record, presence of a claim for a filled prescription does not indicate that the medication was consumed or that it was taken as prescribed. Medications filled over-the-counter or provided as samples by the physician will not be captured in the claims data. The presence of a diagnosis code on a medical claim may not represent true presence of a disease, as the diagnosis code may be incorrectly coded or included as rule-out criteria rather than actual disease.

To assess baseline patient smoking status, diagnosis and procedure codes will be used. Data from published literature²⁴ indicates that while this claims-based algorithm for smoking can identify smokers with very high specificity, its sensitivity is limited, thus suggesting that a large number of true/actual smokers may not be adequately captured in this study.

In addition, due to limitations related to the database, all-cause mortality cannot be assessed since only in-hospital deaths are captured. This may result in an underestimation of the outcome as deaths occurring in other environments (e.g. home, institutions, etc.,) cannot be captured. Additionally, due to privacy concerns, in-hospital deaths cannot be directly captured in the database, and must be estimated via use of an algorithm which will developed as part of this study and will not be able to be validated for use in claims databases. As such, in-hospital deaths may not be accurately captured in this study. For acute events, a 90 day extension period is implemented in part to accommodate ongoing exposure to treatments with longer half lives, and in part to ensure that any subclinical or undiagnosed illness at time of end of treatment is captured. However, there is the possibility of potential misclassification of the exposure window for any treatments for which the half-life is shorter, leading to a potential underestimation of incidence rates for some outcomes.

As tofacitinib is a new UC medication, it is possible that patients treated with it will represent those with the most severe cases of disease, longer disease duration, history of multiple failed

UC therapies and physical comorbidities that place patients at risk for events. Channeling may present as increased rates of safety events of interest in the early phases of the study. Incidence rates from the contexualization cohorts may illuminate such channeling via stratification on key indicators of disease severity such as number of previous biologic treatments, patient characteristics and past therapies. However, certain patient characteristics which may influence VTE risk (e.g. obesity and immobilization), cannot be reliably captured, and thus may limit data interpretation. Trend analyses may be conducted to evaluate rates in tofacitinib patients over time. Analysis may be unable to identify or control for any changes in rates due to changes in the treatment landscape.

Conclusions from this study may be limited to the duration of treatment captured. Finally, while these data may be generalizable to the commercially insured population and patients on Medicare, they may not be representative of those whose primary insurance is through Medicaid.

9.10. Other Aspects

Not applicable.

10. PROTECTION OF HUMAN SUBJECTS

10.1. Patient Information

This study involves data that exist in anonymized structured format and contain no patient personal information.

10.2. Patient Consent

As this study involves anonymized structured data, which according to applicable legal requirements do not contain data subject to privacy laws, obtaining informed consent from patients by Pfizer is not required.

10.3. Institutional review board (IRB)/Independent ethics committee (IEC)

IRB approval will be sought for this protocol by the investigators. There must be prospective approval of the study protocol, protocol amendments, and other relevant documents (e.g., informed consent forms if applicable) from the relevant IRBs/IECs. All correspondence with the IRB/IEC must be retained. Copies of IRB/IEC approvals must be forwarded to Pfizer.

10.4. Ethical conduct of the study

The study will be conducted in accordance with legal and regulatory requirements, as well as with scientific purpose, value and rigor and follow generally accepted research practices described in Guidelines for Good Pharmacoepidemiology Practices (GPP) issued by the International Society for Pharmacoepidemiology, and Good Epidemiological Practice (GEP) guidelines issued by the International Epidemiological Association (IEA).

11. MANAGEMENT AND REPORTING OF ADVERSE EVENTS/ADVERSE REACTIONS

This study involves data that exist as structured data by the time of study start. In these data sources, individual patient data are not retrieved or validated, and it is not possible to link (i.e., identify a potential association between) a particular product and medical event for any individual. Thus, the minimum criteria for reporting an adverse event (AE) (i.e., identifiable patient, identifiable reporter, a suspect product, and event) cannot be met.

12. PLANS FOR DISSEMINATING AND COMMUNICATING STUDY RESULTS

Two interim summary reports and a final study report will be generated and submitted to regulatory authorities where applicable. Data may also be used in regulatory communications external to the US for contextualization purposes. Manuscripts based on specific endpoints of interest may be developed for publication.

In the event of any prohibition or restriction imposed (e.g., clinical hold) by an applicable competent authority in any area of the world, or if the party responsible for collecting data from the participant is aware of any new information which might influence the evaluation of the benefits and risks of a Pfizer product, Pfizer should be informed immediately.

